## 8.5 Exploratory Analysis Excluding Some Study Sites

During the MT-8554-A01, the Sponsor observed a significant degree of study drug non-compliance at a few study sites, where some of these were clustered geographically and had study subjects duplication.

The Sponsor also observed 8 study sites (site number 104, 108, 112, 114, 119, 128, 144, and 158) with significant IP non-compliance based on MT-8554 PK levels. Among them, 4 sites (site number 104, 112, 114, and 119) had highest number of IP non-compliance based on PK levels, were among the high enrollers (site number 112 and 114 were top enrollers and 104 and 119 were among the top 8 enrollers), and were located at a close proximity to each other in the South Florida. The Sponsor initiated a comprehensive re-review to verify the operational conduct of the study.

The Sponsor's review team concluded that at these 4 Florida sites, training and monitoring was conducted similar to all other sites as per standards, and no concerns were identified by the study monitors during the conduct of the study. The Sponsor considered the possibility that the subjects' poor IP compliance could be due to early onset adverse events which might have prevented them from continuation of MT-8554. However, it was noted that there was a lack of adverse events reporting from these 4 Florida sites in comparison to the all others sites. The incidences of AEs at these 4 sites were 31.8, 37.0, 31.6 and 4.3% as compared to 44.1, 39.7, 49.3 and 64.3% at the other sites in placebo, 1, 5, and 10 mg groups respectively, in MT-8554-A01.

Of these 4 sites, one site was identified a duplicate subject during the screening period, which was dropped out of the study. The Sponsor conducted an additional database search to exclude unidentified duplicate subjects. The Sponsor identified 12 subjects at these 4 Florida sites, which were suspected of being duplicates based on date of birth, height, weight medical history, and medications. Later, all these 12 subjects were confirmed by the quality assurance review of the sites as being duplicates, at least one subject at each site.

Therefore, it was considered to conduct the statistical analyses without the data from these sites. As the exploratory analyses, the main efficacy and safety analyses specified as following list will be performed with the ITT and safety population excluding the 4 sites subjects.

No.	Title of Table	Analysis Population
14.1.1.Ex4Site	Subject Disposition and Analysis Population-Exclude 4 Florida site-	All Subjects
14.1.2.Ex4Site	Demography and Baseline Characteristics -Exclude 4 Florida site-	SAF
14.1.5.Ex4Site	Summary of Exposure to Study Medication: Duration of exposure -	SAF

No.	Title of Table	Analysis Population
	Exclude 4 Florida site-	
14.1.6.Ex4Site	Summary of Compliance to Study Medication-Exclude 4 Florida site-	SAF
14.2.1.Ex4Site	Summary of VMS Frequency-Exclude 4 Florida site-	ITT
14.2.2.Ex4Site	Summary of VMS Severity-Exclude 4 Florida site-	ITT
14.2.3.Ex4Site	Summary of Menopause Specific Quality of Life (MENQOL) Domain and Total Scores-Exclude 4 Florida site-	ITT
14.3.1.1.Ex4Site	Summary of Treatment Emergent Adverse Events (TEAE) -Exclude 4 Florida site-	SAF
14.3.1.1.A.Ex4Site	Summary of Treatment Emergent Adverse Events (TEAE) for before the dose change -Exclude 4 Florida site-	SAF
14.3.1.1.B.Ex4Site	Summary of Treatment Emergent Adverse Events (TEAE) for after the dose change -Exclude 4 Florida site-	SAF
14.3.1.2.Ex4Site	Incidence of Treatment Emergent Adverse Events by System Organ Class, Preferred Term-Exclude 4 Florida site-	SAF
14.3.1.2.A.Ex4Site	Incidence of Treatment Emergent Adverse Events by System Organ Class, Preferred Term for before the dose change-Exclude 4 Florida site-	SAF
14.3.1.2.B.Ex4Site	Incidence of Treatment Emergent Adverse Events by System Organ Class, Preferred Term for after the dose change-Exclude 4 Florida site-	SAF
14.3.6.1.Ex4Site	Transvaginal Ultrasound (TVU) -Exclude 4 Florida site-	SAF
14.3.6.2. Ex4Site	Transvaginal Ultrasound (TVU) - Endometrial Thickness-Exclude 4 Florida site-	SAF
14.3.7.1. Ex4Site	Endometrial Biopsy -Exclude 4 Florida site-	SAF

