4.3 Inclusion criteria

A subject will be eligible for enrollment in the study if ALL of the following criteria apply:

1. Signed informed consent to participate in this study.
2. Subjects who complete Study MT-8554-A01 through Week 12.
3. In the Investigator's opinion, subject is able to understand the nature of the study, any risks involved in participation, and is willing to cooperate and comply with the protocol restrictions and requirements including transvaginal ultrasound and endometrial biopsy.

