4.4 Exclusion criteria

A subject will NOT be eligible for this study if the subject meets the withdrawal criteria for Study MT-8554-A01.

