7.3 Subject identification

Each subject will be identified by the unique Subject Number that was assigned to them at the Screening visit of Study MT-8554-A01.

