## **3. STUDY DESIGN**

### **3.1 Study Design**

[figure not shown]
Study MT-8554-A02 is an open-label, long-term safety extension trial of Study MT-8554-A01. The study will be initiated during the conduct of Study MT-8554-A01.

Subjects who complete the preceding trial (Study MT-8554-A01) and comply with eligibility criteria for Study MT-8554-A02 will be enrolled in a 52-week open-label treatment period. Visit 7 (Week 12) of Study MT-8554-A01 will be considered Visit 1 of Study MT-8554-A02. Assessments already carried out at Visit 7 (Week 12) of Study MT-8554-A01 will not be repeated. During the 52-week open-label treatment period, subjects will attend visits every 8 weeks between Visits 1 and 3 (Weeks 12, 20, and 28) and every 12 weeks between Visits 3 and 6 (Weeks 28, 40, 52, and 64).

All enrolled subjects will receive MT-8554 (10 mg initially, switched to 5 mg\*) for 52 weeks. Study drug will be administered once daily before bedtime.

An End of Study (EOS) Follow-up visit will be conducted by phone for safety follow-up 30 days after the end of the open-label treatment period.

\*Note: Based upon the results of Study MT-8554-A01, the dose is changed from 10 mg to 5 mg because participating subjects will no longer derive potential clinical benefit from receiving 10 mg dose. All participating subjects who reconsent to continue the study will receive MT-8554 5 mg.

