**Table 2 Analysis populations**

Analysis Population	Definition
Safety(SAF) population	All subjects who receives at least 1 dose of study medication
Intent-to-treat (ITT) population	All subjects who have at least 1 post-baseline exploratory assessment

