## **6. GENERAL CONSIDERATIONS**

### **6.1 Descriptive Statistics**

Continuous data will be summarized descriptively using the number of observations, mean, standard deviation (SD), median, minimum and maximum. Categorical data will be summarized using frequency counts and percentages. The denominator for the percentages will be the total number of subjects in the treatment group and analysis population being presented, unless otherwise specified.

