## **8. STATISTICAL METHODOLOGY**

### **8.1 Study Subjects**

#### **8.1.1 Disposition of Subjects**

The number of subjects who enter study A02 will be summarized (Table 14.1.1)

Subject disposition will be summarized for subjects completion status and discontinue reasons in tables for each treatment group of MT-8554-A01, and overall.

The data listing for Subject disposition will be generated.

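### Do the 12 duplicate subjects confirmed in A01, and the limited set of four-site exclusion tables, call for a change to the A02 populations or safety tables?

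*SAP*

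**What the plan says.** SAP 8.5 describes what was found in A01. Four sites close to each other in South Florida had the most non-compliance by drug level, were high enrollers and reported fewer adverse events (AEs) than the other sites (4.3% against 64.3% in the 10 mg group). One duplicate found at screening was dropped. A later database search raised 12 more suspects, and "all these 12 subjects were confirmed by the quality assurance review of the sites as being duplicates". The response is a set of exploratory tables without these sites (suffix Ex4Site), limited by its own wording to the main efficacy and safety analyses.

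The rules that decide who is counted in A02 are these:

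- SAP Table 2 defines the safety population as "All subjects who receives at least 1 dose of study medication".
- Protocol 7.3: "Each subject will be identified by the unique Subject Number that was assigned to them at the Screening visit of Study MT-8554-A01".
- Protocol 4.3 admits "Subjects who complete Study MT-8554-A01 through Week 12", and Protocol 4.4 adds: "A subject will NOT be eligible for this study if the subject meets the withdrawal criteria for Study MT-8554-A01".
- SAP 3.1 on timing: "The study will be initiated during the conduct of Study MT-8554-A01".
- SAP 6.1: "The denominator for the percentages will be the total number of subjects in the treatment group and analysis population being presented", unless otherwise specified.
- SAP 8.1.1: "The number of subjects who enter study A02 will be summarized". It does not mention duplicates.

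**The concern.** Long-term safety is the primary objective, and the tables count subject numbers. The A02 entry rules that can be read name no check for duplicates, subjects keep their A01 number, and repeated AEs are collapsed only within a subject (SAP 8.2.1). A02 also opened while A01 was running, and the date of the quality assurance confirmation is not given. A person dosed in A02 under two numbers would therefore appear twice in every all-site table, possibly under two A01 treatment groups.

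The second worry is breadth. The sponsor's reasons for distrusting the four sites apply to serious and threshold events as well. Yet there is no Ex4Site version of the tables for TEAEs leading to discontinuation (14.3.1.5), serious TEAEs (14.3.1.6), laboratory thresholds (14.3.2.6), QTc thresholds (14.3.3.2.2) or the biopsy shift (14.3.7.2). Sites with little drug intake or little reporting would enlarge the denominators and make rare harms look rarer.

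**Working it through.** **1. What a double count needs.** Both records of one person must complete A01 through Week 12, neither may meet the A01 withdrawal criteria (not in these documents), and both must be dosed in A02. The documents are silent on each step for the 12. The number of surplus records in A02 is therefore unknown, and it may be zero.

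**2. Effect on a common event.** Inputs: N = 364 records (ceiling, SAP 3.3) or an assumed 200; s = 12 surplus records, or 6 if the 12 subjects are six pairs; true incidence 50% (assumed). With *a* surplus records carrying an AE:

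observed % = 100 × [0.5 × (N − s) + a] / N

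| N | s | no surplus record has an AE | half do | all do |
|---|---|---|---|---|
| 364 | 12 | 176/364 = 48.4 | 182/364 = 50.0 | 188/364 = 51.6 |
| 364 | 6 | 179/364 = 49.2 | 182/364 = 50.0 | 185/364 = 50.8 |
| 200 | 12 | 94/200 = 47.0 | 100/200 = 50.0 | 106/200 = 53.0 |
| 200 | 6 | 97/200 = 48.5 | 100/200 = 50.0 | 103/200 = 51.5 |

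The error can go either way and vanishes if surplus records report at the common rate. These are overall figures. A single A01-group column would move more only if the surplus records were concentrated in it: all 12 in one column of 91 (364/4, equal split assumed), none with an AE, gives 39.5/91 = 43.4%.

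**3. Effect on a rare event.** With no events among n subjects, the one-sided 95% upper bound is 1 − 0.05^(1/n). Removing 12 records moves it from 0.82% (n = 364) to 0.85% (n = 352). At the target of about 100 completers (Protocol 4.1) it moves from 2.95% to 3.35% (n = 88). One event recorded under both numbers of one person would read 2/364 = 0.55% instead of 1/363 = 0.28%. Serious TEAEs are listed individually, so such a pair can be seen.

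**4. Which tables are uncovered.** SAP 8.2 has 29 readable tables numbered 14.3; five have an Ex4Site version (14.3.1.1, 14.3.1.2, 14.3.6.1, 14.3.6.2, 14.3.7.1) and 24 do not. For the five in question:

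| Table | Related Ex4Site table |
|---|---|
| 14.3.1.5 discontinuation TEAEs | events are a subset of 14.3.1.2; possibly a row in 14.3.1.1 (shell not shown) |
| 14.3.1.6 serious TEAEs | same |
| 14.3.7.2 biopsy shift | same biopsies as 14.3.7.1, cross-tabulated against baseline |
| 14.3.2.6 laboratory thresholds | none |
| 14.3.3.2.2 QTc thresholds | none |

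**5. Size for the uncovered tables.** Let f be the four-site share of A02 (not given) and r the four-site rate divided by the other-site rate. Dropping the sites multiplies the percentage by 1/(1 − f + f × r). If r = 1 the factor is 1.00. If r = 0 it is 1.05, 1.11, 1.25 or 1.33 for f = 5, 10, 20 or 25%. At the last of these, five cases read 5/364 = 1.4% with all sites and 5/273 = 1.8% without. The A01 10 mg AE ratio, 4.3/64.3 = 0.067, would give 1/(0.75 + 0.25 × 0.067) = 1.30 at f = 25%. That ratio concerns reported AEs by A01 dose. Laboratory values and QTc are measured, so it does not scale them.

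**The case for a change.** The strongest case for acting is that the SAP raises the matter itself and then leaves it open. Its database search was meant to exclude duplicates, but that is a purpose and not a population rule. If the number that entered A02 is zero, one sentence would say so. The two threshold tables have no Ex4Site counterpart of any kind, because a laboratory or ECG abnormality reaches the TEAE tables only if the investigator judges it clinically significant (Protocol 6.5.4, 6.5.7). Poor drug intake at these sites, as distinct from poor reporting, could also dilute a real effect on measured values. Two of the sites were top enrollers and the other two were among the top eight, so their share of A02 may not be trivial.

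All of this stands as description. It does not show an error. A merging rule written in advance would also be less simple than it sounds. Study days run from A01 randomization (SAP Table 1, note 2), so a merged person could have two Day 1s, two baselines, two diaries and overlapping dosing. Those choices are better made on actual cases, if there are any. A sentence about duplicates, or two more sensitivity tables, would be harmless. Protocol 10.3.1 already allows additional analyses and requires deviations from plan to be explained in the study report.

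**Conclusion.** No change is needed. The silence on duplicates is a gap that analysts fill sensibly: a person is one subject, and a confirmed double enrolment would be counted once and reported. The records known to be duplicates sit at four named sites, which are already removed from the Ex4Site tables for disposition, demography, exposure, compliance, efficacy, TEAEs, endometrial thickness and biopsy.

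The breadth of that set is a fair choice. It is labelled exploratory and confined to main analyses, and three of the five tables at issue largely re-cut data it already covers. For the two that do not, the full laboratory and ECG data are listed.

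The size in A02 is unknown. On the extreme assumption that 12 surplus records entered, a 50% overall incidence is off by at most 1.6 percentage points at 364 records, or 3 points at an assumed 200. For the two threshold tables the factor is at most 1.33, assuming a 25% four-site share and no case there. There is no formal sample size, so no decision threshold rests on these percentages. The conclusion would change only if many people were found to have been dosed in A02 under two numbers and were still left counted twice.

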## 9. DATA PRESENTATION CONVENTIONS

### 9.1 Number of Digits to Report

**Table 7 Number of decimal places (DP) or significant digits (SD)**

Statistic	Specification	Apply to
Minimum, maximum	same number of DPs as the data provided in the datasets	All original, i.e. non-derived, data provided in the datasets
	See section 7.3	All derived data
Mean, Median	one more DP than above	All
SD, SE	two more DP than above	All
Percentages*	1 DP	All

\*Percentages: use 1 place beyond the decimal point, except for the following cases:

If the percentage is equal to 0, then leave blank, do not use (0)

If the percentage is equal to 100, then use "(100)" without a decimal

Listings will be presented in subject, visit (where applicable) and date (where applicable) order. Listings will be produced (landscape in MS Word) using PROC REPORT in SAS monospace font and pitch 8.

Summary tabulations will be presented by treatment group of study A01 and overall if appropriate, scheduled visit order (if appropriate). Continuous data summaries will present (unless stated otherwise) number of observations, mean, standard deviation, median, minimum and maximum. Categorical data summaries will present the number of observations and the corresponding percentage.

## **10. CHANGE FROM THE PROTOCOL**

Protocol says “Baseline VMS severity score is defined as  $(2xFmo + 3xFse)/(Fmo + Fse)$ , and VMS severity score for a specific week during the open label treatment period is defined as  $(1xFmi + 2xFmo + 3xFse)/(Fmi + Fmo + Fse)$ , where Fmi, Fmo, and Fse are the daily frequencies of mild, moderate, and severe VMS, respectively, during each applicable study week.”. However, the baseline VMS severity score is from the end of treatment of study A01. The VMS severity score there is defined as  $(1xFmi + 2xFmo + 3xFse)/(Fmi + Fmo + Fse)$ . So this formula is used for baseline VMS severity score in A02.

## **11. SOFTWARE**

The statistical evaluation will be performed using SAS® Version 9.4 or later.
